3.3 INTERVENTION

Eligible participants will be randomly assigned into one of three study arms: 1) 4.5 mg naltrexone, 2) up to 1800mg gabapentin, or 3) placebo. Study medication will be provided by trained physicians, who will instruct participants in proper medication administration and adherence.

Drug capsules containing naltrexone hydrochloride (4.5mg), gabapentin (300 mg), and placebo will be prepared by NonStopPharma, a compounding pharmacy in St. Petersburg, Russia. Doses will look identical; participants and providers will be blinded to assigned medication. Participants will be instructed to take anywhere from one capsule per day to two capsules orally three times per day for 8 weeks. If a participant in any group experiences an adverse event, the dosage will be decreased by one capsule. Participants will be given 14 days' worth of medications at the baseline visit, 7 days' worth of medications at the 1-week visit, 14 days' worth of medications at the 2-week visit, 14 days' worth of

medications at the 4-week visit, and 7 days' worth of medications at the 6-week visit, with instructions to bring pill packs/leftover medications to the following visit.

The Food and Drug Administration (FDA) has indicated that an Investigational New Drug (IND) is not needed for studies conducted outside the United States.

3.3.A. NALTREXONE

Participants randomized to this group will receive low-dose naltrexone for 8 weeks.

Participants will be instructed to take the medication from one to three times daily for 8 weeks. Each daily pill pack for participants in the low-dose naltrexone arm will contain one capsule of low-dose naltrexone (4.5mg) and the appropriate number of placebo capsules. Depending on the week, the number of placebo capsules per day will range between one and six, to match the dosage of the gabapentin arm. Naltrexone dosing will start on the day of the baseline visit, after successful passing of the naloxone challenge. If the participant does not pass the naloxone challenge, he/she will be brought back within a week to try again.

Medication will be packaged in pill boxes. Participants will receive 1 box of 7 capsules and 1 box of 21 capsules at baseline (14 days worth of medication), at the 1-week visit participants will receive 1 box of 42 capsules, at the 2-week visit participants will receive 2 boxes of 42 capsules, at the 4-week visit participants will receive 2 boxes of 42 capsules; at the 6-week visit participants will receive 1 box of 33 capsules. In week 1, participants will take 4.5mg of naltrexone once daily. In week 2, participants will take 4.5mg of naltrexone once daily. In weeks 3 through 7, participants will take 1 placebo capsule with 4.5 mg mg of naltrexone once daily, and 2 placebo capsules twice daily. In week 8, in days 1-4 participants will take 4.5 mg of naltrexone with a placebo capsule once daily and 2 placebo capsules twice daily; in days 5-7, participants will take 4.5 mg of naltrexone once daily, and a placebo capsule twice daily.

The most common side effects (reported in more than 1 in 10 people) of naltrexone are difficulty sleeping, anxiety, nervousness, abdominal pain/cramps, nausea and/or vomiting, low energy, joint and muscle pain, and headache.

Uncommon side effects (reported in less than 1 and 10 people, but more than 1 in 100 people) of naltrexone are loss of appetite, diarrhea, constipation, increased thirst, increased energy, feeling down, irritability, dizziness, skin rash, delayed ejaculation, decreased potency, and chills.

Rare side effects (reported in less than 1 in 100 people) of naltrexone include nasal congestion, itching, rhinorrhea, sneezing, sore throat, excess mucus or phlegm, sinus trouble, heavy breathing, hoarseness, cough, shortness of breath, nose bleeds, phlebitis, edema, increased blood pressure, non-specific ECG changes, palpitations, tachycardia, excessive gas, hemorrhoids, diarrhea, ulcer, painful shoulders, legs or knees; tremors, twitching, increased frequency of, or discomfort during, urination; increased or decreased sexual interest, oily skin, pruritus, acne, athlete's foot, cold sores, alopecia, depression, paranoia, fatigue, restlessness, confusion, disorientation, hallucinations, nightmares, bad dreams, eyes—

blurred, burning, light sensitive, swollen, aching, strained; ears—"clogged," aching, tinnitus, Increased appetite, weight loss, weight gain, yawning, somnolence, fever, and dry mouth,

Please note that these side effects were reported among people taking 50mg of naltrexone. This study will use low dose naltrexone (4.5mg) and side effects are expected to be milder. In order to help prevent these adverse effects, participants will be instructed not to take more medication than what is provided by the study. Study clinicians will also be monitoring for signs of naltrexone overdose. These adverse effects are not expected to be likely.

3.3.B. GABAPENTIN

Participants randomized to this group will receive gabapentin for 8 weeks.

Gabapentin dosing will start on the day of the baseline visit after successful passing of the naloxone challenge. If the participant does not pass the naloxone challenge, he/she will be brought back within a week to try again.

Participants will be instructed to take the medication from one to three times daily for 8 weeks. Medication will be packaged in pill boxes. Participants will receive 1 box of 7 capsules and 1 box of 21 capsules at baseline (14 days worth of medication), at the 1-week visit participants will receive 1 box of 42 capsules, at the 2-week visit participants will receive 2 boxes of 42 capsules, at the 4-week visit participants will receive 2 boxes of 42 capsules; at the 6-week visit participants will receive 1 box of 33 capsules.

Participants randomized to the gabapentin arm begin on a dose of 300 mg daily (300 mg qd). In week 2, participants will take 300 mg of gabapentin three times daily. In week 3 the dose will be titrated up to 1800 mg daily (300 mg+300 mg tid) will remain on the dose until week 8, when they will be tapered back down to 900 mg daily (300 mg tid). In week 8, in days 1-4 participants will take 1800 mg daily (300 mg+300 mg tid); in days 5-7, participants will take 900 mg daily (300 mg of gabapentin three times daily). Gabapentin will only be titrated up as tolerated by the participant. Participants will be monitored regularly for side effects and medication tolerability (weeks 1, 2, 4, 6, and 7) If a participant experiences adverse effects while on medication, the participant's dose will be reduced down to the previous dose (or to a lower dose that the participant can tolerate). Research Assessors in this study are all trained addiction psychiatrists, with experience in clinical trials and adverse event monitoring.

The most common side effects (frequency of side effects cannot be estimated from available data) of gabapentin are lack of coordination, feeling tired, viral infection, fever, feeling drowsy, jerky movements, nausea and vomiting, difficulty with coordination, difficulty with speaking, double vision, tremor, unusual eye movement, and swelling (usually of legs and feet).

Rare side effects of gabapentin (reported in about 1 in 500) include suicidal thoughts or actions. These may include thoughts about suicide or dying, attempts to commit suicide, new or worse depression, new or worse anxiety, feeling agitated or restless, panic attacks, trouble sleeping (insomnia), new or worse

irritability, acting aggressive, being angry, or violent, acting on dangerous impulses, an extreme increase in activity and talking (mania), other unusual changes in behavior or mood.

Other side effects (frequency of side effects cannot be estimated from available data) of gabapentin are serious or life-threatening allergic reactions that may affect one's skin or other parts of the body such as the liver or blood cells. Symptoms may include skin rash, hives, difficulty breathing, fever, swollen glands that do not go away, swelling of the face, lips, throat, or tongue, yellowing of the skin or of the whites of the eyes, unusual bruising or bleeding, severe fatigue or weakness, unexpected muscle pain, frequent infections.

3.3.C. PLACEBO

Participants randomized to this group will receive a placebo medication for 8 weeks.

Medication dosing will start on the day of the baseline visit after successful passing of the naloxone challenge. If the participant does not pass the naloxone challenge, he/she will be brought back within a week to try again.

Participants will be instructed to take the medication one to three times daily for 8 weeks. Medication will be packaged in pill boxes. Participants will receive 1 box of 7 capsules and 1 box of 21 capsules at baseline (14 days worth of medication), at the 1-week visit participants will receive 1 box of 42 capsules, at the 2-week visit participants will receive 2 boxes of 42 capsules, at the 4-week visit participants will receive 2 boxes of 42 capsules; at the 6-week visit participants will receive 1 box of 33 capsules.

In week 1, participants will take 1 placebo capsule once daily. In week 2, participants will take 1 placebo capsule three times per day. In week 3 through 7, 2 placebo capsules three times per day. In week 8, in days 1-4 participants will take 2 placebo capsules three times per day; in days 5-7, participants will take 1 placebo capsule three times per day. The placebo medications will be composed of lactose and will not contain active ingredients. The placebo and active study medications will be indistinguishable by appearance and taste.

3.3.D. NALOXONE CHALLENGE

At the baseline visit, participants will be administered the naloxone challenge and observed for signs of opioid withdrawal for 20 minutes. Naloxone blocks the effects of opioids. It works only if it is injected and lasts about 30 minutes. It is used in hospitals and by emergency services to reverse the effects of a heroin or other opioid overdose. It will cause withdrawal if injected into someone who is currently physically dependent on opioids and will be administered to make sure that the participant is not physically dependent on heroin or other opioids before s/he is given oral naltrexone. The naloxone challenge will only be administered if the information the participant provides to the staff indicates that s/he is not physically dependent on heroin or other opioids and if his/her urine drug test is negative. The challenge will be done by administering 0.8-mg naloxone slowly intramuscularly. The participant will be observed by a research assessor for signs of withdrawal for 5-20 minutes.

Discomfort during the naloxone challenge will occur if the participant is physically dependent on opioids. Naloxone can induce opioid withdrawal, such as feeling sick, stomach cramps, muscle spasms, feelings of

coldness, heart pounding, muscular tension, aches and pains, yawning, runny eyes, and insomnia. If participants have withdrawal after the naloxone test, their symptoms may be treated with 150mcg clonidine or 2mg of phenazepam orally and are not anticipated to last more than 45-60 minutes. As withdrawal symptoms precipitated by naloxone typically resolve within 20 minutes without treatment, use of these medications will be decided on a case-by-case basis by the treating Russian physician-investigator.

The most frequent side effects (which appear to be dose-related) of clonidine are dry mouth, occurring in about 40 of 100 patients; drowsiness, about 33 in 100; dizziness, about 16 in 100; constipation and sedation, each about 10 in 100.

The following less frequent adverse experiences have also been reported in patients receiving clonidine tablets, but in many cases patients were receiving concomitant medication and a causal relationship has not been established: fatigue, fever, headache, pallor, weakness, and withdrawal syndrome. Also reported were a weakly positive Coombs test and increased sensitivity to alcohol, bradycardia, congestive heart failure, electrocardiographic abnormalities (i.e., sinus node arrest, junctional bradycardia, high degree AV block and arrhythmias), orthostatic symptoms, palpitations, Raynaud's phenomenon, syncope, and tachycardia. Cases of sinus bradycardia and atrioventricular block have been reported, both with and without the use of concomitant digitalis, agitation, anxiety, delirium, delusional perception, hallucinations (including visual and auditory), insomnia, mental depression, nervousness, other behavioral changes, paresthesia, restlessness, sleep disorder, and vivid dreams or nightmares, alopecia, angioneurotic edema, hives, pruritus, rash, and urticaria, abdominal pain, anorexia, constipation, hepatitis, malaise, mild transient abnormalities in liver function tests, nausea, parotitis, pseudo-obstruction (including colonic pseudo-obstruction), salivary gland pain, vomiting, decreased sexual activity, difficulty in micturition, erectile dysfunction, loss of libido, nocturia, and urinary retention, thrombocytopenia, gynecomastia, transient elevation of blood glucose or serum creatinine phosphokinase, weight gain, leg cramps and muscle or joint pain, dryness of the nasal mucosa, accommodation disorder, blurred vision, burning of the eyes, decreased lacrimation, and dryness of eyes.

The most frequent side effects of phenazepam use are drowsiness, sedation, muscle weakness, and ataxia. These side effects generally decrease on continued administration and are a consequence of CNS depression.

Less frequent effects include vertigo, headache, confusion, depression, slurred speech or dysarthria, changes in libido, tremor, visual disturbances, urinary retention or incontinence, gastrointestinal disturbances, changes in salivation, and amnesia. Some patients may experience a paradoxical excitation, which may lead to hostility, aggression, and disinhibition.

Jaundice, blood disorders and hypersensitivity reactions have been reported rarely. Raised liver enzyme values have occurred.

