If the participant fails the naloxone challenge, s/he will be invited to come back within a week to repeat the challenge. Participants who pass the naloxone challenge will then complete the study assessment, cold-pressor testing and be randomly assigned to either low-dose naltrexone, gabapentin, or placebo. Study medication will be provided by trained physicians, who will instruct participants in proper medication administration and adherence.

Study participants, investigators, staff, and physicians administering the medications will be unaware of specific group assignment.

Participants will be treated for 8 weeks, and observed for 4 weeks post-treatment. Outcomes (pain severity and interference (BPI), biomarkers IL-6, 1 β , IL-10, and TNF- α , cold pain tolerance, percentage of past month heavy drinking days, CD4 cell count, and HIV viral load) will be evaluated at the end of treatment.

Throughout the course of the study, participants will be expected to come in for eight in-person assessments. The schedule of study in-person visits/assessments are as follows: baseline, 1, 2, 4, 6, 7, 8, and 12 weeks. At week 4, we will assess for medication tolerability, discontinuation, treatment side effects, self-reported adherence to intervention medications, and pain (BPI) only. At week 8, we will assess pain (BPI), biomarker IL-6, IL-1 β , IL-10, and TNF- α levels, cold pain tolerance using cold-pressor, pain interference, percentage of past month heavy drinking days, and HIV control (CD4 cell count & HIV viral load). At week 12 (post-treatment), there will be an assessment of pain (BPI) and cold-pressor test to assess whether pain reverts back to pre-treatment levels. Weeks 1, 2, 6, and 7 will be short visits, at which a brief assessment of tolerability, side effects, and adherence will occur, and we will ensure that participants have their medications (e.g. have not been lost or stolen).

Visits will be preceded by phone/text reminders to the participant or alternate contacts.

The text message will read: "This is a reminder that your visit to Pavlov Medical University is scheduled for____at___. Please reply to confirm or call [name] to reschedule."

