3.4 MEDICATION CONSIDERATIONS

3.4.A SYMPTOM MONITORING

The study staff (research clinicians [addiction physicians with extensive experience performing pharmacotherapy trials]) will provide participants with the correct medication packages and advice on how to take the capsules. The staff will be trained to assess for adverse medication effects and will follow established protocols for identifying and monitoring any ongoing adverse events, including referral to treatment as appropriate. Study participants will be actively monitored for adverse events. Symptoms will be assessed every two weeks (and monitored more frequently, if necessary) by trained clinical staff, while the participants are administered study medications. Processes have be set up to address any adverse event brought to the attention of study staff during the trial.

3.4.B. ADHERENCE

As one of the study outcomes, medication adherence will be assessed at each study visit using the following measures.

Capsule Counts

Participants will be instructed to bring any unused medication to each study visit post-baseline. The RA will count and record the number of remaining capsules. We will extrapolate the amount of medication taken and determine the measure of adherence.

Self-Report

Medication adherence will also be measured through self-report using the modified Adult AIDS Clinical Trial Group (AACTG) ART adherence questions.

Pill Diary

Participants will be asked to keep a daily written record ("daily diary") of pain severity, medication adherence, and alcohol use.

Adherence Aids

During each study visit medication instructions will be reviewed and strategies for adherence discussed with each participant. Adherence plans will be individually tailored to each participant, depending on his or her reason for non-adherence.

Participants will also be encouraged to set a reminder in their phone to take the study medication three times each day.

3.4.C. MEDICATION DISBURSEMENT

Medication inserts will be provided to participants at baseline.

Medication distribution will be as follows:

Naltrexone:

- 7 capsules/box, 1 capsule/day (Week 1)
 - o Week 1: 4.5 mg qd (4.5 mg total)
- 21 capsules/box, 3 capsules/day (Week 2)
 - Week 2: 4.5 mg naltrexone qd, 1 placebo capsule bid
- 42 capsules/box, 6 capsules/day (Week 3-7)
 - Weeks 3-7: 1 placebo to be taken with 4.5 mg naltrexone qd, 2 placebo capsules to be taken bid
- 33 capsules/box, (Week 8)

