6.1. SPECIFICATION OF SAFETY PARAMETERS

An **Adverse Event (AE)** is defined as any untoward or unfavorable medical occurrence in a human subject, including any abnormal sign (for example, abnormal physical exam or laboratory finding), symptom, or disease, temporally associated with the subject's participation in the research, whether or not considered related to the subject's participation in the research.

An AE can therefore be any new sign, reaction, symptom, event, disease or a worsening in frequency or severity of a preexisting condition that occurs during the course of the study.

Stable chronic conditions that were present prior to study entry and do not worsen are not considered AEs.

SERIOUS Adverse Event (SAE) – for an event to be defined as serious, it will be Grade 1-6 below. Grade 0 would be "not serious".

Grade (1) results in death;

Grade (2) is life-threatening (places the subject at immediate risk of death from the event as it occurred);

Grade (3) results in inpatient hospitalization or prolongation of existing hospitalization;

Grade (4) results in a persistent or significant disability/incapacity;

Grade (5) results in a congenital anomaly/birth defect; or

Grade (6) based upon appropriate medical judgment, may jeopardize the subject's health and may require medical or surgical intervention to prevent one of the other outcomes listed in this definition (examples of such events include allergic bronchospasm requiring intensive treatment in the emergency room or at home, blood dyscrasias or convulsions that do not result in inpatient hospitalization, or the development of drug dependency or drug abuse).

Unanticipated Problem (UP) – for an event to be an Unanticipated Problem it must

- be unexpected AND
- be related or possibly related to participation in the research AND
- suggest that the research places subjects or others at a greater risk of harm (including physical, psychological, economic, or social harm) than was previously known or recognized. OR meet the definition of SERIOUS

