The study will take place in a medical setting where standard procedures are in place to assist patients who experience acute events. If consequences arise due to research procedures (e.g. distress, anxiety, suicidal thoughts,) the physician investigators will be available to assess participants and make appropriate interventions or referrals based on the clinical circumstances. Any participant who voices current suicidality, is experiencing a psychiatric emergency, or expresses the intent to harm others during the assessments will be reported to an on-site physician, immediately. That physician will determine the appropriate course of action, which will depend on location of the event and the clinical situation. Patients will be escorted to receive care by appropriate staff if deemed necessary.

- If an event is discovered outside of the scheduled study visits, it must still be recorded accordingly.
- Action Taken will be determined by the RAs for all AEs that are Mild and Moderate (unless specified below) and by [name] or [name] for SAEs and AEs that are severe, life-threatening or fatal.

6.3. PROCEDURES FOR ELICITING REPORTS OF AND FOR RECORDING AND REPORTING ADVERSE EVENT AND INTERCURRENT ILLNESSES

For any reported side effect: While with the participant, study personnel will listen, identify, and document the symptoms. The following symptoms will be assessed at baseline and during medication check-ins and study visits while participant is taking the study medication. All events will be documented on the Symptom Checklist and on AE forms.

Symptom
Agitation and/or Irritability
Anger
Depressed mood
Anxiety (includes nervousness and panic attacks)
Insomnia and/or other sleep problems
Abnormal dreams and/or nightmares
Headaches
Dizziness/lack of coordination
Nausea and/or vomiting
Joint/muscle pain
Abdominal pain/cramps

Fatigue
Drowsiness
Difficult speaking
Tremor
Jerky movements
Fever
Double vision
Swelling (legs or feet)
Unusual eye movement

6.3.A. OTHER EVENTS

- Other events may or may not be associated with study drug use, but will be recorded, AE form completed and [name] or [name] will be notified immediately to address the report.
- [name] or [name] will evaluate the reported symptoms using clinical judgment to determine if they are related to the study and if study medication should be adjusted or ceased.

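### Two dose-reduction rules give different doses with no stated precedence, and in the naltrexone arm the one-capsule cut either changes nothing or stops the drug

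*Combined protocol and SAP*

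**What the plan says.** The combined protocol and SAP has two rules for lowering the dose.

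- Section 3.3, all arms: "If a participant in any group experiences an adverse event, the dosage will be decreased by one capsule".
- Section 3.3.B, gabapentin: a participant with adverse effects has the dose "reduced down to the previous dose (or to a lower dose that the participant can tolerate".

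Neither refers to the other. On blinding, section 3.1 says "Study participants, investigators, staff, and physicians administering the medications will be unaware of specific group assignment". Section 3.3 says "Doses will look identical; participants and providers will be blinded to assigned medication", and 3.3.C adds "The placebo and active study medications will be indistinguishable by appearance and taste".

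In the naltrexone arm, each day's capsules include one 4.5 mg naltrexone capsule and placebo capsules to match the gabapentin count. Section 3.4.C gives the main treatment period as "Weeks 3-7: 1 placebo to be taken with 4.5 mg naltrexone qd, 2 placebo capsules to be taken bid".

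The trigger is also described in more than one way. Section 3.3 acts on an adverse event, which 6.1 defines "whether or not considered related to the subject's participation in the research". Section 6.2 says "Action Taken will be determined by the RAs for all AEs that are Mild and Moderate (unless specified below", and 6.3.A leaves dose adjustment for other events to clinical judgment.

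**The concern.** These rules decide what a participant with side effects takes next. Two assessors could each follow the text and give the same gabapentin participant different doses. The usual answer, that the specific rule overrides the general one, does not work here: the specific rule depends on the arm, and the plan keeps the arm from everyone who would apply it.

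The naltrexone arm has a further problem. Taking one capsule from a set of look-alikes with a single active member is not a dose reduction. It either leaves the dose as it was, in someone who has reported side effects, or withdraws the drug. Naltrexone versus placebo is one of the two primary comparisons, and section 2.7.A says that the pilot is mainly for estimating effects to plan a larger trial. It therefore matters whether participants counted as on naltrexone were taking it.

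**Working it through.** **Inputs.** Gabapentin capsules are 300 mg (3.3). The levels are 1, 3 and 6 capsules a day: 300 mg in week 1, 900 mg in week 2, and 1800 mg in weeks 3 to 7 and on days 1 to 4 of week 8. Days 5 to 7 of week 8 return to 900 mg (3.3.B, 3.4.C). The naltrexone arm has one active capsule a day throughout (3.3.A, 3.4.C).

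**The plan's supply figures reproduce** for the gabapentin and naltrexone lists in 3.4.C. Weeks 1 and 2 need 7×1 + 7×3 = 28 capsules, matching the boxes of 7 and 21. Week 8 needs 4×6 + 3×3 = 33, as stated. The course needs 7 + 21 + 35×6 + 33 = 271, and 7 + 21 + 42 + 84 + 84 + 33 = 271 are dispensed. The capsule counts used below are therefore the plan's own.

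**Gabapentin after one reduction:**

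| Level before | 3.3: one capsule off the day's total | 3.3, other reading: one off each of three daily doses | 3.3.B default: previous level |
|---|---|---|---|
| 6 capsules, 1800 mg | (6−1)×300 = 1500 mg | (6−3)×300 = 900 mg | 900 mg |
| 3 capsules, 900 mg | (3−1)×300 = 600 mg | (3−3)×300 = 0 mg | 300 mg |
| 1 capsule, 300 mg | 0 mg | not applicable (one daily dose) | none exists |

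The bracketed option in 3.3.B can mean lower than the previous dose or lower than the current dose. On the second meaning, 1500 mg and 600 mg satisfy both rules.

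**Packaging.** Five capsules a day is 35 a week and two a day is 14 a week. The weekly boxes hold 7, 21 or 42, or 33 for week 8. The one-capsule rule can therefore be carried out with existing boxes only by leaving a capsule out.

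**Naltrexone after a one-capsule cut:**

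- Week 1: the single capsule is the active one, so 1−1 leaves 0 mg. The same cut leaves nothing in the other two arms.
- Weeks 2 to 8: one of 3 or one of 6 capsules is active. Leaving out a placebo capsule keeps 4.5 mg; leaving out the active one gives 0 mg. No dose in between exists.
- Over the 35 days of weeks 3 to 7, days without naltrexone run from 0 (always omitting from a twice-daily dose) to 35 (always omitting the active capsule). The plan does not say which capsule to omit.

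**What the records show.** Capsule counts and the diary (3.4.B) and the action entered on the adverse event form (6.3.B) would show that the dose was cut and how many capsules came back. None identifies whether the omitted capsule was active.

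**The case against.** Several points on the other side stand.

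- *The rules need not conflict everywhere.* They overlap if the lower dose in 3.3.B means lower than the current one. On the per-dose reading they agree at 1800 mg, the scheduled dose for 35 + 4 = 39 of 56 days. A reader might infer a contradiction at every level on every reading; the text does not support that. What remains is that the plan does not choose a reading, and the default in 3.3.B differs from the plain reading of 3.3.
- *Judgment is provided for.* Sections 6.2 and 6.3.A leave much to trained clinicians, so it would be too strong to say that every adverse event automatically cuts the dose. The sentence in 3.3 is nevertheless unconditional.
- *Week 1.* The sentence before the one-capsule rule gives one capsule a day as the bottom of the dosing range, which can be read as a floor. Without that floor, all three arms go to zero. Week 1 is not a defect specific to naltrexone.
- *Unrecorded loss of drug.* A reader might infer this, but reductions are recorded. Only the identity of the omitted capsule is not.
- *Dilution.* One naltrexone participant at zero throughout would be 1/13 = 7.7% of the assumed completers, and 3.8/13 = 0.29 points. But 3.8 is the plan's minimum detectable difference, not an expected effect, and 0.29 compares with a planned confidence interval width of 4.7. It also assumes no drug at all and no effect without it. Analysis is by intention to treat, so dose changes are part of what is estimated. The figure illustrates scale and does not show bias.
- *Visit windows and the week-1 hand-out.* The week-1 window runs to day 10, while the 900 mg step falls on day 7. Sections 2.3 and 3.5 omit a hand-out that 3.3, 3.4.C and 4.4 include. One might infer unsafe escalation, but the target visit is day 7, titration is conditional on tolerance, and an in-window visit on drug always precedes 1800 mg. These are minor clarifications outside this point.

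None of this rescues the one-capsule rule in the naltrexone arm.

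**Conclusion.** The point holds as a defect in a stated rule. The two instructions have no order of precedence, and under the plan's own blinding statements an arm-specific rule cannot be applied. On the plain reading the gap after one step is 1500 − 900 = 600 mg a day from 1800 mg and 600 − 300 = 300 mg a day from 900 mg. This takes one capsule as one off the daily total and the previous level as the default in 3.3.B.

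In weeks 2 to 8 a one-capsule cut in the naltrexone arm leaves 4.5 mg or gives 0 mg, and neither staff nor the records can tell which. This follows from the capsule lists and needs no assumption about frequency. The consequence for the naltrexone estimate is unknown, because the documents give no rate of dose reduction and do not say which capsule is left out. It is worth correcting because the rule sets dosing in a primary comparison and the repair is small, not because a material bias has been shown.

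**What to change.** Delete the one-capsule sentence in 3.3 and put one blinded rule for all arms in its place:

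- Step down to the previous box level, from 6 to 3 to 1 capsules a day, by exchanging boxes and not by leaving capsules out. The 42-, 21- and 7-capsule boxes already exist, and in the naltrexone arm each holds one naltrexone capsule per day. For gabapentin this matches the default in 3.3.B.
- Apply it to events that the assessor judges not tolerated.
- A participant who does not tolerate one capsule a day stops study medication and is followed under 3.4.E.
- State openly that naltrexone therefore stays at 4.5 mg or is stopped. This does not create a lower naltrexone dose, and the sponsor should confirm that this is acceptable. Section 3.3.A already expects milder side effects at 4.5 mg than at 50 mg.

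The cost is one deleted sentence, a few added in 3.3 and 3.4.C, some spare 7- and 21-capsule boxes per arm, and an occasional exchange visit. A participant stepped down to three a day from the start of week 3 would need at most six 21-capsule boxes (weeks 3 to 8). Section 3.4.D already foresees extra supply for lost medication. No new box type is needed.
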